Official title: Dose-response of physical exercise on pelvic floor muscle function in postmenopausal women with urinary incontinence

Number: NCT04351750

Document date: 12/22/2021

Study protocol

Urinary incontinence (UI) symptoms are highly prevalent among women, and menopause may be a risk of developing urinary incontinence¹. During the menopausal transition, not only the hormonal secretion is changed but also the physical activity is affected. The time women spend in physical activity is reduced and the time spent in sedentary behavior is increased in postmenopausal women². Studies have shown that physical activity acts in a bidirectional manner, exerting either a preventive or an aggravating effect on urinary incontinence³. Individuals with sedentary lifestyle and insufficient physical activity (< 150 min/week) are at risk of developing UI, and regular physical activity exerts a protective effect in preventing UI, but the optimal type, duration, and intensity of exercise for the female older adult population remain unknown. In addition, objective measurements of pelvic floor muscle function was needed as the use of self-reported measures may cause response bias⁴. The aim of the study was to investigate the effect of different intensity of exercise on pelvic floor muscle function and health-related quality of life (HRQoL) in postmenopausal women with UI. We hypothesized that (a) both high- and low-intensity physical activities could improve pelvic floor muscle strength and HRQoL in postmenopausal women with UI, and (b) the improvement in high-intensity group would be higher than that in low-intensity group. A randomized trial was conducted to compare the effect of different exercise intensity on pelvic floor muscle function in postmenopausal women with UI (n=38). The participants were randomly allocated to high-intensity group, low-intensity group or control group. Each group received an 8-week intervention. Both high-intensity group and low-intensity group received a multimodal exercise program including aerobic exercise, resistance exercise, and pelvic floor muscle training. The control group underwent only pelvic floor muscle training. The outcome measures including pelvic floor muscle function, UI symptom severity, HRQoL,

voiding function, and physical activity levels were assessed at baseline and after 8-week intervention.

Statistical analysis plan

Data analysis was performed by Statistical Product and Service Solutions (SPSS) version 22.0 (SPSS, Chicago, IL, USA). The descriptive data were presented as mean, standard deviation (SD), number and percentage. The one-way ANOVA tests were used to compare the continuous data between two groups and chi-square tests were used for categorical data. Shapiro-wilk tests were used to assess the normality of data. Paired-t tests and McNemar's test were used for within-group comparisons. The repeated-measure ANOVA tests and chi-square tests were used to compare changes in outcomes between groups after intervention; ANCOVA tests were used if adjustment for significant differences between groups on outcomes at baseline was needed. A significant level was set at p-value<0.05.

Reference

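### The intensity question can be answered only by high versus low, but the SAP names only a comparison across groups, which can be significant with no intensity effect

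*Combined protocol and SAP*

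**What the plan says.** The official title reads "Dose-response of physical exercise on pelvic floor muscle function in postmenopausal women with urinary incontinence". The term dose-response appears there and nowhere else in the document.

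The Study protocol section puts the aim in terms of intensity: "The aim of the study was to investigate the effect of different intensity of exercise on pelvic floor muscle function". Hypothesis (b) is a comparison of two arms: "b) the improvement in high-intensity group would be higher than that in low-intensity group".

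There are three randomised arms: "The participants were randomly allocated to high-intensity group, low-intensity group or control group". Their content is given in two sentences: "Both high-intensity group and low-intensity group received a multimodal exercise program including aerobic exercise, resistance exercise, and pelvic floor muscle training" and "The control group underwent only pelvic floor muscle training". Outcomes "were assessed at baseline and after 8-week intervention", so there are two time points. The total sample is 38. Numbers per arm, the allocation ratio, the intensity levels, session length and frequency are not given.

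The Statistical analysis plan section assigns the between-group comparison of changes to repeated-measures ANOVA (chi-square for categorical outcomes), with ANCOVA if a baseline imbalance needs adjustment, at the 0.05 level. It names no high-versus-low contrast, no post-hoc procedure and no trend test.

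**The concern.** The three arms differ in two ways. From low to high, the components stay the same and the intensity rises. From control to low, two kinds of exercise are added. The first step bears on the aim and on hypothesis (b). The second answers a different question: whether a multimodal programme adds anything to pelvic floor muscle training.

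A test across all three groups responds to either step. If the programme helps but its intensity is irrelevant, the test can still reach significance. Nothing in the SAP then tells the reader that this result does not bear on hypothesis (b). The trial could credit intensity with an effect that belongs to programme content.

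The title adds a smaller difficulty. Two non-zero intensity levels yield one difference, and one difference cannot show the shape of a dose-response.

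**Working it through.** The plan states no power, effect size or SD, so there is no figure of its own to reproduce.

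**Inputs from the documents.** Three arms, a total of 38, two time points, significance level 0.05.

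**Assumptions.** Control 12, low 13, high 13; normally distributed change scores with a common SD of 1; two-sided testing; no dropout. Effects are in SD units of the change score.

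**Step 1: what the three-group test responds to.** With two time points, the group-by-time F of a repeated-measures ANOVA equals the one-way ANOVA F on change scores. Let d be the mean of the exercise arms minus control, and e be high minus low. The noncentrality splits into two parts:

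λ = [n_C(n_L + n_H)/N]·d² + [n_L·n_H/(n_L + n_H)]·e²
= (12 × 26/38)·d² + (13 × 13/26)·e²
= 8.21·d² + 6.5·e²

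Only the second part concerns intensity.

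**Step 2: no intensity effect (e = 0).** The test rejects when F on 2 and 35 degrees of freedom exceeds 3.27. The noncentral F distribution and a simulation of 40,000 trials per setting agree:

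| d (SD) | λ = 8.21·d² | three-group test significant | high versus low significant |
|---|---|---|---|
| 0.5 | 2.05 | 21% | 5% |
| 0.8 | 5.25 | 49% | 5% |
| 1.0 | 8.21 | 69% | 5% |

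The three-group test is correctly rejecting equality of three means. The error would be to read that rejection as evidence for hypothesis (b).

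**Step 3: sensitivity to the split.** With control 13, low 13 and high 12, the simulated three-group figures are 22%, 50% and 71%. With 8, 15 and 15 they are 17%, 39% and 57%. High versus low stays at about 5% in both.

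**Step 4: what the high-versus-low contrast can deliver.** At 13 per arm:

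- 95% confidence interval half-width: t(0.975; 24 df) × √(1/13 + 1/13) = 2.064 × 0.392 = 0.81 SD.
- Power (noncentral t): 23% at a true difference of 0.5 SD, 50% at 0.8 SD, 69% at 1.0 SD.
- Difference detectable with 80% power: about 1.15 SD.
- For 80% power by the normal approximation, about 63 per arm would be needed at 0.5 SD and 25 per arm at 0.8 SD.

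**The case against.** The strongest reply is that hypothesis (b) already states the right comparison. High and low were both randomised and contain the same components, so their difference is not confounded by content. This stands. The trial can address intensity, provided the two programmes differ in nothing else, which the documents do not spell out. What is missing is the named test in the SAP.

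One might find that test in the SAP's mention of one-way ANOVA for continuous data between two groups. That sentence does not say which two of the three groups or which data. Comparisons of change after the intervention are assigned elsewhere, to the repeated-measures ANOVA.

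A second reply is that the title speaks of physical exercise, not intensity. All arms had pelvic floor muscle training, so control can be read as zero added exercise. This is a fair reading, and it weakens any complaint about the title. Even so, control to low is absence versus presence of two components. It says nothing about intensity, and the stated aim is about intensity.

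A reader might go further and infer that the plan will declare a dose-response whenever the means fall in the order control, low, high. With no intensity effect, ordered means together with a significant three-group test would occur in about 10% of trials at 0.5 SD and about 35% at 1.0 SD (12/13/13 split). The documents do not support treating these as error rates of the plan, because it states no ordered-means rule and no trend test. The percentages also reflect the chance ordering of two equal arms, and a plateau on a single dose scale would produce the same ones. They illustrate a possible misreading and no more.

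**Conclusion.** The point holds as a gap between the question and the named analysis. The aim and hypothesis (b) depend on high versus low, and the SAP's only named test of between-group change is across groups. With no intensity effect, that test is significant in about 21% to 69% of trials for programme effects of 0.5 to 1.0 SD, against 5% for the direct contrast. The range rests on assumed arm sizes, normal change scores and assumed effects. The qualitative point needs none of these, since the first term of λ is positive whenever the exercise arms together differ from control.

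The documents do not support saying that the randomised comparison of intensities is confounded, or that the sponsor planned to infer a dose-response from the ordering of means. The wording of the title is a secondary matter.

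**What to change.** In the SAP:

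1. Test hypothesis (b) by the high-versus-low contrast on change from baseline and report the estimate with its 95% confidence interval. Use the same contrast where ANCOVA applies, and the same two arms for categorical outcomes.
2. Report the exercise arms versus control separately, as the effect of adding aerobic and resistance exercise to pelvic floor muscle training.
3. State that a significant three-group result alone will not be read as an effect of intensity.

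In the report, describe the result as a comparison of two exercise intensities, because two non-zero levels cannot show the shape of a dose-response.

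The protocol is written in the past tense, so the arms are fixed. The change needs no new data or participants. Its cost is a narrower headline and an openly imprecise answer on intensity: at about 13 per arm the interval extends about 0.8 SD either side of the estimate, and a non-significant contrast would not show that the two intensities are equivalent.

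### Baseline adjustment depends on a low-power significance test, and the SAP does not say whether baseline physical activity would adjust the strength and HRQoL comparisons

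*Combined protocol and SAP*

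**What the plan says.** The Study protocol section randomises 38 postmenopausal women with UI to three arms: "The participants were randomly allocated to high-intensity group, low-intensity group or control group". It gives no allocation ratio and mentions no stratification. One of its two hypotheses is that "the improvement in high-intensity group would be higher than that in low-intensity group".

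The background links habitual activity to the condition under study. It describes activity as able to prevent or worsen incontinence and says that "Individuals with sedentary lifestyle and insufficient physical activity (< 150 min/week) are at risk of developing UI". Activity is also in the list of outcome measures: "voiding function, and physical activity levels were assessed at baseline and after 8-week intervention".

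The Statistical analysis plan section compares changes between groups by repeated-measures ANOVA. Its only provision for baseline adjustment is conditional: "ANCOVA tests were used if adjustment for significant differences between groups on outcomes at baseline was needed". It names no covariates. Since activity is a listed outcome, a significant activity difference could come under this rule. The text does not say which models would then be adjusted.

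**The concern.** The intervention is exercise, so the exercise a woman already does is a natural candidate to predict her response. It is a different covariate from the outcome's own baseline value. With about 13 women per arm, chance can leave the high- and low-intensity arms noticeably different in habitual activity. If activity is related to the change in strength or HRQoL, that difference moves the very contrast the second hypothesis is about.

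The SAP's safeguard acts only when a baseline test is significant, and at this size such a test seldom is. Even when it is, the covariate set is left open, so two analysts following the text could fit different models. At stake are the precision of the high-versus-low estimate and how well it is protected in the one trial that was run.

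**Working it through.** **Inputs from the documents.** Total 38 women, three arms, significance level 0.05, activity measured at baseline. No sample-size calculation, SD or effect size is given, so there is no planned figure to reproduce.

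**Assumptions.** Arms of 13/13/12, simple randomisation, baseline activity roughly normal and expressed in SD units, two-sided tests. The correlation r between baseline activity and the change in outcome is not in the documents; 0.1, 0.3 and 0.5 are used as a range.

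**1. How large a chance imbalance is.** The SD of the high-minus-low difference in mean baseline activity is √(1/13 + 1/13) = √(2/13) = 0.39. Then P(|difference| > 0.5) = 2 × [1 − Φ(0.5/0.392)] = 0.20, and P(|difference| > 0.8) = 0.04. With 12 per arm the figures are 0.41, 0.22 and 0.05.

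**2. How often the trigger catches it.**
- With the control arm midway between the other two, the three-arm ANOVA reaches p < 0.05 only when the observed high-low gap is about 1.0 SD. A pairwise t test needs t(0.975, 24 df) × √(2/13) = 0.81 SD.
- In simulated trials (arms 13/13/12) with a high-low gap above 0.5 SD, the three-arm ANOVA was significant in about 17%, so about 83% would go unadjusted. A pairwise t test flagged about 25%. This agrees with 0.05/0.20 = 0.25, since every gap it flags is, in practice, above 0.5 SD.
- The mean gap in these trials was 0.69 SD.

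**3. What an unadjusted gap does to the outcome contrast.** The shift is r × gap, in SDs of the change in outcome.

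| r | gap 0.5 SD | gap 0.69 SD |
|---|---|---|
| 0.1 | 0.05 | 0.07 |
| 0.3 | 0.15 | 0.21 |
| 0.5 | 0.25 | 0.34 |

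**4. Type I error.** Over all simulated trials it is about 5% without the covariate (0.048 at r = 0.3, 0.052 at r = 0.5) and with it (0.050, 0.051). Within the trials whose gap exceeds 0.5 SD, the unadjusted test rejects a true null in about 7.0% (r = 0.3) or 10.6% (r = 0.5); with the covariate the rate stays near 5%.

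**5. What fixed adjustment costs and gains.** With three arms the within-arm residual df is 35. Adding one normal covariate multiplies the variance of the high-low contrast by (1 − r²) × (1 + 1/33) = (1 − r²) × 34/33.
- r = 0: 1.03
- r = 0.2: 0.99
- r = 0.3: 0.94
- r = 0.5: 0.77

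Break-even is where 1 − r² = 33/34, so r = √(1/34) = 0.17. If the outcome's own baseline is already in the model, r is the partial correlation and the factor becomes (1 − r²) × 33/32, which is practically the same.

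**The case against.** The strongest reply is that randomisation already deals with this. Any activity imbalance is due to chance, the standard error allows for it, and step 4 shows about 5% type I error overall either way. That stands, and it rules out calling the problem bias. It does not justify the trigger, because in an imbalanced trial the adjusted estimate is the better one and the trigger usually withholds it.

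A second reply is that the SAP compares changes, so a stable link between activity and the level of strength cancels. This also stands: only a link with response matters, which is how r is defined above, and its size is unknown. Across all trials the mean absolute gap is about 0.39 × 0.80 = 0.31 SD, a shift of about 0.09 SD at r = 0.3 against a contrast SE near 0.39 SD. The typical effect is modest, and below r of about 0.17 adjustment loses slightly.

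Three stronger readings might be inferred, and the documents do not support them.
- *The trial enrolled the wrong population because its rationale is about women below 150 min/week.* That clause is background on the risk of developing UI. The same sentence gives the gap as "the optimal type, duration, and intensity of exercise for the female older adult population remain unknown", which fits the stated aim.
- *Women of any activity level could enter.* The text contains no eligibility list, so this rests on silence alone.
- *Activity plays no part in adjustment.* The conditional rule can be read to cover it; the text is ambiguous on the point.

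One limitation of the remedy also stands. If the effect of intensity differs by prior activity, a single main-effect term does not describe that difference.

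**Conclusion.** The point holds as a weakness of the adjustment rule. The SAP makes baseline adjustment depend on a significance test that, at 38 women in three arms, misses about 83% of high-low activity gaps above 0.5 SD. It also leaves open whether activity would enter the strength and HRQoL models at all. About one trial in five has a gap of that size. The consequence is lost precision and weaker protection against chance imbalance. There is no systematic bias and no inflation of the overall error rate.

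The detection figures rest on the assumed near-equal arms and a roughly normal covariate. The shift in the contrast and the precision gain also rest on r, for which only a range can be shown. This is an inexpensive improvement and does not by itself invalidate the comparison.

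**What to change.** Remove the significance trigger. In the between-group models for pelvic floor muscle strength and HRQoL, include the outcome's own baseline value and the baseline physical activity level as fixed covariates, whatever a baseline test shows. Use activity in whatever unit it was recorded, since the documents name neither instrument nor unit. Never use the week-8 activity value, which the assigned programme may itself have changed. Report baseline activity by arm.

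The document is written in the past tense. If the data have already been analysed, the adjusted model cannot be presented as pre-specified and should be labelled a supportive analysis next to the one reported.

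The cost is a change of SAP wording and one model term for activity, using data already collected, with no new participants or procedures. The statistical downside is one residual degree of freedom: about 3% more variance if activity is unrelated to response, and a net gain once r exceeds about 0.17.

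### No pairwise contrast is named for either hypothesis, and the within-arm tests cannot show what exercise adds to the pelvic floor training that every arm receives

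*Combined protocol and SAP*

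**What the plan says.** The Study protocol section gives the aim: "The aim of the study was to investigate the effect of different intensity of exercise on pelvic floor muscle function", together with quality of life (HRQoL). Two hypotheses follow:

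- (a) "both high- and low-intensity physical activities could improve pelvic floor muscle strength and HRQoL in postmenopausal women with UI". No comparator is stated.
- (b) "the improvement in high-intensity group would be higher than that in low-intensity group". The comparator is explicit.

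Thirty-eight women are randomised to three arms and assessed at baseline and after 8 weeks. On the exercise arms: "Both high-intensity group and low-intensity group received a multimodal exercise program including aerobic exercise, resistance exercise, and pelvic floor muscle training". On the third arm: "The control group underwent only pelvic floor muscle training".

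The Statistical analysis plan section names three relevant procedures:

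- Within arms: "Paired-t tests and McNemar's test were used for within-group comparisons".
- Between arms: "The repeated-measure ANOVA tests and chi-square tests were used to compare changes in outcomes between groups after intervention".
- Adjustment for baseline: "ANCOVA tests were used if adjustment for significant differences between groups on outcomes at baseline was needed".

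None of these is tied to (a) or (b). The sentence on one-way ANOVA speaks of comparing two groups, but it does not say which two, and it is separate from the sentence on change after the intervention. Significance is set at 0.05. No multiplicity rule is given.

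**The concern.** The only tests in the plan that are specific to one arm are the within-arm tests. An arm's change from baseline mixes the added aerobic and resistance exercise with pelvic floor training, regression to the mean and repeat testing. Only the randomised comparison with the training-only control separates the added exercise from the rest.

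The repeated-measures ANOVA includes the control. With no contrast named, it reads as a global three-group test, which can be significant when only one intensity differs and does not show which. The same gap affects (b), because no high-minus-low difference is named.

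At stake is interpretation. Two significant paired tests, with or without a significant global test, could be taken to show that both intensities work when one or neither adds anything to pelvic floor training.

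**Working it through.** **Inputs.** From the documents: 38 women, three arms, two time points, significance level 0.05. The plan states no SD, effect size, power or allocation ratio, so there is no figure of its own to reproduce. Assumed: a 13/13/12 split in any order, two-sided tests, normally distributed changes with equal SD, and gains in units of the SD of change. Results are for one continuous outcome unless stated.

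**1. Hypotheses against named tests**

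| Question | Named procedure | Does it answer the question? |
|---|---|---|
| (a) as change within each arm | Paired t, McNemar | Yes, as description only |
| (a) as benefit over control | Global ANOVA | Not for each intensity |
| (b) high over low | Global ANOVA | Not for that pair |

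**2. Paired tests when exercise adds nothing.** All three arms gain the same amount d. In an arm of size n, the paired t statistic is noncentral t with n − 1 df and noncentrality d × √n. For d = 0.8 and n = 13, the noncentrality is 0.8 × √13 = 2.88 and the power is 0.754. The exercise arms are independent, so the chance that both are significant is the product of their powers.

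| Shared gain (SD) | n = 12 | n = 13 | Both (12 and 13) | Both (13 and 13) |
|---|---|---|---|---|
| 0.3 | 0.158 | 0.169 | 0.027 | 0.029 |
| 0.5 | 0.353 | 0.382 | 0.135 | 0.146 |
| 0.8 | 0.714 | 0.754 | 0.538 | 0.569 |
| 1.0 | 0.883 | 0.911 | 0.804 | 0.829 |

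**3. Global test.** With two time points, the group-by-time test equals one-way ANOVA on change scores. It rejects in 5% of trials when exercise adds nothing. If only high intensity works, adding 1.0 SD, then the global test and both paired tests are all significant in 9 to 63% of simulated trials for shared gains of 0.3 to 1.0 SD. Both contrasts against control are significant in favour of exercise in only about 2.5%.

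**4. Precision of a contrast.** Unadjusted, the 95% CI half-width is t(0.975, 35) × √(1/13 + 1/12) = 2.03 × 0.400 = 0.81 SD of change. ANCOVA multiplies the SD by about √((1 + ρ)/2), where ρ is the baseline-to-8-week correlation. That factor is 0.87 for ρ = 0.5 and 0.92 for ρ = 0.7, giving about 0.70 and 0.75. Simulated half-widths are 0.70 to 0.76.

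**5. Power for both control contrasts** (equal true benefit in both exercise arms; ANCOVA with assumed ρ of 0.5 to 0.7)

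| True added benefit (SD) | Unadjusted | Conditional ANCOVA rule | ANCOVA always |
|---|---|---|---|
| 0.5 | 11% | 11% | 13–15% |
| 0.8 | 34% | 34% | 39–46% |
| 1.0 | 54% | 55% | 61–69% |

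Under randomisation the baseline test is significant in about 5% of trials per outcome, so the conditional rule performs almost like no adjustment.

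**6. Single-intensity claims.** With no added benefit, at least one of the two unadjusted control contrasts is significant in about 9% of trials (4.5% in favour of exercise). Across two outcomes this is 16 to 17% (8 to 9% in favour), for an assumed between-outcome correlation of 0 to 0.5.

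**The case against.** The strongest reply is that (a) most simply asks whether each arm improved from its own baseline. Hypothesis (b) speaks of the improvement in an arm and compares two such improvements. On that reading the paired tests match (a), and what is left is a missing label and a caution about interpretation. This reading is at least as natural as benefit over control, and it stands. It does not make within-arm change an effect of the added exercise.

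Three stronger inferences are not supported by the documents.

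- A reader might infer that the plan has no comparison with control. It has one, in the repeated-measures ANOVA and the conditional ANCOVA. Pairwise follow-up is unnamed but not excluded.
- A reader might infer that efficacy will be claimed from paired tests. The plan nowhere says so, and combining the global test with both paired tests is only a possible way of reading results.
- A reader might infer that the aim requires each intensity to be compared with control. Its wording points first to high versus low.

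Two further objections also stand. The magnitudes rest on assumed gains, allocation and correlations. The conditional ANCOVA rule does not cause the missing contrasts; it belongs here because the contrasts need a model, and always adjusting gives better precision.

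**Conclusion.** The point holds in a limited form. The plan names no pairwise contrast for either hypothesis. Its only arm-specific tests cannot separate added aerobic and resistance exercise from the pelvic floor training common to all arms.

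The 13% to 83% for shared gains of 0.5 to 1.0 SD (about 3% at 0.3 SD) shows how often both paired tests would be significant with no added benefit. These results are false positives only if (a) is taken as benefit beyond pelvic floor training. They are not an error rate of the plan. If (a) means change within each arm, the tests describe that change correctly.

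The figures assume near-equal allocation, normal changes with equal SD, and one continuous outcome. That no contrast compares the whole programme with no treatment is a limit of the design, which analysis cannot remove.

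**What to change.** 1. Label paired t and McNemar results descriptive, and report them only as change after the programme. State whether (a) was meant as change within arm or as benefit over control.
2. For any claim that an intensity is effective, or that high exceeds low, report the high-minus-control, low-minus-control and high-minus-low differences at 8 weeks with 95% CIs, separately for strength and HRQoL. The repeated-measures ANOVA can stay as the global test.
3. Estimate these differences by ANCOVA on the baseline value in every case, in place of the rule triggered by a significant baseline difference.
4. Claim benefit for both intensities on an outcome only if both control contrasts are significant in favour of exercise. Apply an adjustment such as Holm to single-intensity claims and to claims where either outcome suffices. State whether a claim requires both outcomes.
5. The document is written in the past tense, so label as post hoc any contrast or rule fixed after the data were seen.

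**Cost.** No new data and a little more analysis. Power for the joint claim on one outcome is low, as shown in step 5 of the working. If strength and HRQoL must both succeed (four contrasts), it falls with ANCOVA to about 2 to 5%, 15 to 28% and 37 to 53% for 0.5, 0.8 and 1.0 SD. For one contrast without baseline adjustment, assuming 38/3 = 12.67 women per arm, testing at 0.025 (the first Holm step for two tests) rather than 0.05 lowers power from about 23%, 49% and 67% to 15%, 37% and 56%. With intervals of about ±0.70 to 0.76 SD, a non-significant contrast does not show absence of benefit. The estimates and CIs should carry the conclusion.

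### Does the chi-square test fail to hold the 5% level with only 38 women in three groups?

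*Combined protocol and SAP*

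**What the plan says.** The section Study protocol gives the trial's size, "pelvic floor muscle function in postmenopausal women with UI (n=38", and its three groups: "The participants were randomly allocated to high-intensity group, low-intensity group or control group". It gives no allocation ratio. It lists the outcome domains without saying which are categorical, how many categories they have or what proportions are expected.

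The section Statistical analysis plan names one between-group test for categorical variables. In general, "chi-square tests were used for categorical data"; for outcomes after the intervention, "The repeated-measure ANOVA tests and chi-square tests were used to compare changes in outcomes between groups after intervention". Within-group categorical comparisons use McNemar's test. The threshold is stated once: "A significant level was set at p-value<0.05". The section mentions no exact test, continuity correction or rule for sparse tables.

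**The concern.** The chi-square test relies on a large-sample approximation, and the usual teaching is to distrust it when expected counts fall below 5. With about 12 or 13 women per group that will often happen. A reader would reasonably suspect that the 5% level is not delivered: too strict for uncommon or very common categories, and too lenient elsewhere. If the test were lenient, group differences in categorical outcomes could be declared on evidence weaker than claimed. If it were badly strict, real differences could be missed in an already small trial. The obvious remedy would be to require exact tests throughout.

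**Working it through.** **Inputs.** Total 38, three groups and threshold 0.05 come from the document. The split 13/13/12 is an assumption (near-equal allocation). The proportions below are also assumptions and are shown as a range, since the document gives none.

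**Step 1: the expected-count rule.** The smallest expected count in a binary table is 12 × T/38 or 12 × (38 − T)/38, where T is the number of women with the outcome.
- T = 15: 12 × 15/38 = 4.74, below 5.
- T = 16: 12 × 16/38 = 5.05, above 5.

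By symmetry the rule is met for T = 16 to 22, that is 16/38 = 42.1% to 22/38 = 57.9%. This part of the concern is right.

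**Step 2: does breaking the rule damage the test?** There are 14 × 14 × 13 = 2,548 possible binary tables. For each, compute X² = Σ (aᵢ − nᵢp̂)² / [nᵢp̂(1 − p̂)], with aᵢ women with the outcome in group i and p̂ = T/38. Reject if X² is at least 5.99 (2 degrees of freedom). The true size is the summed binomial probability of the rejected tables under a common proportion. The Fisher-Freeman-Halton exact test is evaluated on the same tables.

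| Common proportion | Chance of an expected count below 5 | Chi-square size | Exact-test size |
|---|---|---|---|
| 5% | over 99% | 1.99% | 0.80% |
| 10% | over 99% | 3.74% | 2.26% |
| 20% | 99.8% | 4.31% | 3.96% |
| 30% | 92% | 4.63% | 4.45% |
| 40% | 55% | 4.96% | 4.45% |
| 50% | 26% | 5.05% | 4.42% |

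Proportions above 50% mirror those below. At 30%, 92% of tables break the rule, yet the size is 4.63%. The size is 4.1% at a proportion of 15%, so it is close to nominal from about 15% to 85%, and it falls towards zero only near the extremes. The maximum is 5.05%.

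**Step 3: sensitivity to the assumed split.** The same enumeration for other splits of 38 gives maximum sizes of 5.2% (14/14/10), 5.5% (14/12/12), 5.0% (16/12/10) and 5.1% (18/10/10). No split tried gives material inflation.

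**Step 4: two-group comparisons.** Uncorrected chi-square for 13 v 13 has size 1.8% at a proportion of 10% and 7.6% at 50%. At 50% every expected count is 13 × 0.5 = 6.5, so the inflation lies inside the range that the expected-count rule calls safe. It comes from the discreteness of two equal groups. For 13 v 12 the maximum is 5.3%. Under 13/13/12 only one of the three pairs is 13 v 13.

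**Step 5: would an exact test do better?** By the table, the exact test is more conservative at every proportion, most of all for uncommon outcomes. For two groups of 13, Fisher's test never exceeds 2.9%. Power can also fall: with true proportions 10%, 10% and 50%, it is 69% for chi-square and 62% for the exact test when the 50% group is the one of 12. When the 50% group is one of 13, the two are almost level (66.6% and 66.2%).

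**The case for a change.** The strongest reply is that average size hides what happens in a single table. With events 0/3/0, X² = 1.11 + 4.12 + 1.03 = 6.26 and chi-square p = 0.044. The exact p is (286 + 286 + 220)/8436 = 0.094, the chance that all three events fall in one group. With 4/5/0 the order reverses: 0.059 against 0.048. Given the total number of events, chi-square size ranges from 0% to 9.4%, the highest at exactly 3 (or 35) events. These figures are correct. But the two tests disagree at 0.05 in only 38 of the 2,548 tables (30 significant by chi-square only, 8 by the exact test only). At a proportion of 8%, where 0.08 × 38 = 3.04 events are expected, overall chi-square size is still 3.3%. Whether to control error for each fixed event total or over repeated trials is a long-standing disagreement; the plan is not wrong to follow the second view.

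It can also be said that the second hypothesis sets high against low intensity, so two-group categorical tests are plausible. They are, but the plan does not specify them. Its reference to two groups is attached to the ANOVA for continuous data, and that hypothesis concerns muscle strength and quality of life, neither of which is said to be categorical.

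Outcomes with three categories would have sparser cells. For an assumed 60/30/10 distribution about 62% of cells fall below an expected 5, yet size is about 4.1%; for an assumed 85/10/5 it is about 2.5%. The error is again conservative.

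What stands is that the SAP is brief: it does not name its categorical outcomes, say how sparse tables would be handled, or say which version of McNemar's test is meant. That is missing detail and does not make the chosen test invalid.

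**Conclusion.** The concern does not hold. Low expected counts are near-certain for many outcomes at this sample size, but they do not make the planned three-group chi-square test liberal. Under an assumed 13/13/12 split and a binary outcome its true size never exceeds 5.05%, and over the other splits tried it stays at or below 5.5%. The conservatism for rare or very common outcomes is real (2.0% at a proportion of 5%), but a conditional exact test would deepen it (0.8%). The 7.6% figure belongs to an uncorrected 13 v 13 comparison that is outside the stated plan, and the expected-count rule does not predict it. Replacing chi-square with exact tests throughout trades stricter control in individual tables for more conservatism and, in some settings, lower power, and statisticians differ on that trade. The conclusion rests on near-equal allocation, on the omnibus three-group reading of the post-intervention comparison, and on assumed proportions, because the document identifies no categorical outcome to which the concern could be tied.
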